We plan to enroll up to 3 leaders/staff and up to 15 youth/YA participants working with one organization.

Phase 2

We plan to enroll up to 3 leaders/staff from each of four organizations (two of the organizations will receive the intervention, two will be control groups). For each organization randomized to receive the intervention, we will also enroll up to 60 youth/YA participants.

Total

Across both phases, we plan to enroll up to 15 organizational leaders/staff and up to 120 youth/YA participants, for a total possible N of up to 135 people.

Interventions and Interactions

All interviews will be conducted by study staff and may occur in-person, by telephone, or by video call, based on logistical considerations and participant preference. Interviews will be audio-recorded for transcription purposes. Interviews may be conducted individually or in groups and should last 30 minutes, and no more than 60 minutes. All surveys will be completed electronically via REDCap and should last around 20 minutes. Study staff will also periodically conduct and audio-record problem-solving check-ins with organizational leaders/staff.

Phase 1

For organizations, feasibility data will be collected of organization leaders/staff who are involved in implementing the YE strategy, via one survey and one interview per leader/staff. The organization will be paid \$250 for their participation in the open trial. This token of appreciation is for the leaders/staff's time spent engaging with study staff and providing feasibility data through interviews and written feedback.

Study staff will administer (or we will train organization staff to administer) surveys via REDCap to assess their impressions of their YE work as well as constructs such as self-efficacy, connection, and knowledge about substances. Each survey should require no more than 30 minutes each and youth/YA participants will be paid a \$15 gift card (e.g., Amazon) upon completion. The YE strategy manual will be revised based on information learned from the feasibility data.

The timeframe for this phase will be 6-12 months.

Phase 2

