We will follow similar interview and survey data collection procedures as in Phase 1, with adaptations as needed based on participant feedback. However, only organizations randomized to treatment will include youth/YA participants. Youth/YA survey data will be collected at the start of their participation in the YE strategy (pre-YE) and 6 months later (post-YE). At the post-YE we will interview a subset of interested YE group participants to qualitatively assess their experiences and to identify, in their own voices, what aspects of YE emerge as important to youth development and their health-related decision-making. Youth/YAs will be paid \$10 for the pre-YE survey, \$15 for the post-YE survey, and \$25 for an interview (for a subset of youth/YA), for a maximum total of \$50 in gift cards.

The timeframe for this phase will be 12-18 months.

Outcome Measure(s)

Phase 1

For organizations, information collected from staff via surveys and interviews will include: the facilitators and barriers of incorporating YE into prevention, the acceptability

of the strategy, evaluation of the support and resources available and what else would be needed to successfully implement YE, and perceived usefulness for YAs and the organization.

For the youth/YAs, information collected via surveys will include: skills (e.g., leadership, communication) and attitudes (e.g., self-efficacy, social connectedness, self-confidence, meaningful social role) as well as knowledge and views of substance misuse. In interviews, we will ask youth/YAs about the facilitators and barriers of participating in the prevention effort, the acceptability of the YE strategy, evaluation of the experience working with the community organization, and likelihood of continued participation. For both organizations and individuals, feasibility data will be collected regarding retention of youth/YAs in the prevention work.

Phase 2

For organizations, information collected from staff via surveys and interviews will include: perceived value added to prevention programming; retention of YAs in prevention programming; reach of prevention efforts in the community; perceived usefulness of YE to the organization, the YAs, and to the community; and perceived effectiveness of incorporating YE into prevention efforts.

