For the youth/YAs, information collected will include: skills (e.g., leadership, communication) and attitudes (e.g., self-efficacy, social connectedness, self-confidence, meaningful social role) as well as knowledge and views of substance misuse. The outcomes will be measured through self-reported surveys. These will serve as benchmarks that the YE intervention has the intended effect at the individual (psychosocial) level.

Analytical Plan

Phase 1 will examine descriptive statistics collected via surveys (from organizational staff and youth/YAs) and exploratory themes collected from interviews.

Phase 2 analyses will examine the effects of the YE prevention strategy on *organization* level outcomes such as perceived value of YE added to prevention programming, and secondarily, on *individual* level skills and attitudes of the youth/YAs involved in the YE. We hypothesize that YE-involved youth/YAs will show gains in skills (leadership, communication) and attitudes (self-efficacy, social connectedness, self-confidence, meaningful social role) as well as more knowledge and less favorable views of opioid misuse (compared to “pre” measures). These data will be used to estimate the effect sizes needed to power a larger study. These data will serve as additional information about the recruitment, feasibility, retention, fidelity and acceptability of the intervention. Comparison between groups will be done using chi square tests for proportions, and t-tests or ANOVA procedures for continuous variables. Regression analysis will be performed to identify independent outcome predictors. Other inferential statistical analysis will be conducted as appropriate.

Human Subjects Protection

Subject Recruitment Methods

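### The plan does not say how youth with only a pre-YE survey enter the pre/post comparison; if survey return depends on the starting score, either t-test reading biases the gain and the effect size carried forward.

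*Combined protocol and SAP*

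**What the plan says.** Under Interventions and Interactions, Phase 2, "only organizations randomized to treatment will include youth/YA participants", and "Youth/YA survey data will be collected at the start of their participation in the YE strategy (pre-YE) and 6 months later (post-YE"). Sample size allows up to 60 youth in each of two treatment organizations. Confidentiality and Privacy provides for linking each youth's two surveys.

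The Analytical Plan states the youth hypothesis as gains "compared to “pre” measures", so the youth comparison is within one group over time. On method, for comparison between groups, it names chi-square tests where the outcome is a proportion, and "t-tests or ANOVA procedures for continuous variables". It adds regression to look for outcome predictors, and then: "Other inferential statistical analysis will be conducted as appropriate". On the purpose of the results it says: "These data will be used to estimate the effect sizes needed to power a larger study".

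The document gives no expected return rate for the 6-month survey, no analysis set for youth with one survey, no missing-data method, and no planned comparison of returners with non-returners. Retention of young people in the prevention work is listed as an outcome, but that is a different quantity: a youth can leave the programme and still answer the survey, or stay and not answer.

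**The concern.** With no control youth, no second arm can offset selective return, and any distortion stays whole in the estimated gain. The named tests offer two obvious ways to analyse the surveys. A paired t-test, or classical repeated-measures ANOVA, drops every youth without a post-YE survey and with them a pre-YE score already collected. An unpaired t-test or one-way ANOVA keeps every survey but compares the post-YE mean of returners with the pre-YE mean of everyone. Neither uses the pre-YE scores to correct for who came back, and nothing in the test output would show the problem.

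At stake are the test of the youth hypothesis and the effect size passed to the larger study. Planned sample size varies as one over the square of that effect size, so a modest error in the gain becomes a large one in the later study.

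**Working it through.** The plan has no statistical figure of its own to reproduce: it states no significance level, power, SD, effect size or return rate. All numerical inputs below except the maximum N are therefore assumptions.

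**Inputs.** Maximum youth N: 2 × 60 = 120 (Sample size). Assumed: true gain G = 0.30 SD; equal SDs at the two surveys, so that the slope of post on pre equals the correlation r; r = 0.5 or 0.7; return of 60% or 80%; log-odds of return changing by ±0.5 per SD of pre-YE score (a factor of e^0.5 = 1.65).

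**Formulas.** Let m be the returners' mean pre-YE score minus the mean of all youth, in SD. If return depends only on the pre-YE score:

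- paired gain in returners = G − (1 − r)m
- unpaired, returners' post minus everyone's pre = G + r·m
- likelihood model using every pre-YE score = G

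The paired estimate is unbiased if m = 0 or r = 1. The unpaired estimate is unbiased if m = 0 or r = 0. For r strictly between 0 and 1 and m not zero, both are biased, with opposite signs.

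**Size of m.** For a standard normal pre-YE score and logistic return, m = ±0.189 at 60% return and ±0.096 at 80%.

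| Return | r | Paired: high / low scorers return more | Unpaired: high / low scorers return more |
|---|---|---|---|
| 60% | 0.5 | 0.205 / 0.395 | 0.395 / 0.205 |
| 60% | 0.7 | 0.243 / 0.357 | 0.432 / 0.168 |
| 80% | 0.5 | 0.252 / 0.348 | 0.348 / 0.252 |
| 80% | 0.7 | 0.271 / 0.329 | 0.367 / 0.233 |
| any | any, m = 0 | 0.300 | 0.300 |

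Example, first row: 0.30 − (1 − 0.5) × 0.189 = 0.205. Simulation of 2,000,000 pairs per scenario agreed with the paired column to within about 0.002, and the baseline-adjusted estimate was 0.299 to 0.300.

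**Effect on a later study.** At r = 0.5 and 60% return the paired result changes planned size by (0.30/0.205)² = 2.1 or (0.30/0.395)² = 0.58. At r = 0.7 and 80% return the factors are (0.30/0.271)² = 1.2 or (0.30/0.329)² = 0.83.

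**A stronger dependence.** With a 2-fold change in odds per SD, r = 0.5, 60% return and n = 120 (4,000 simulated trials), the paired gain is 0.18 or 0.43. With two-sided 5% significance and 80% power, a later two-arm study moves from 175 per arm to about 499 or 87. With no true gain, the paired test rejects in about 19% of trials instead of 5%.

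**Bias beside sampling error.** The SD of the change is √(2(1 − r)), which is 1 at r = 0.5. With all 120 youth enrolled, 60% return leaves 72 pairs and a standard error of 1/√72 = 0.12, against a bias of 0.095. At 80% there are 96 pairs and a standard error of 1/√96 = 0.10, against a bias of 0.048.

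**The case against.** A reader might infer that the plan commits to a paired test that can use only youth with both surveys. The documents do not support that. The t-test and ANOVA are named for comparison between groups, pairing is not stated, and no test is named for pre/post change. An unpaired test would use every survey, and the open clause on other inferential analysis would allow a mixed model. What remains is that the unpaired reading is biased too, and that a permission is not a commitment: the choice would be made after the data are seen.

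A reader might also infer that the gain will be biased, or by a known amount. That is not supported either. Every figure for size and direction is conditional on assumed return, correlation and selectivity. In the mildest selective case shown for the paired test the shift is about 0.03 SD, and it is zero if return is unrelated to the pre-YE score and to the gain.

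The pilot is small, the youth outcomes come second to the organization outcomes, and with at most 120 youth the effect size will be imprecise anyway: the 95% interval half-width at r = 0.5 is about 1.96 × 0.12 = 0.23 at 60% return and 1.96 × 0.10 = 0.20 at 80%. This stands as a reason for proportion. It does not remove the point, because a confidence interval shows sampling error and does not show this bias, and the effect size is a stated product of the pilot.

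**Conclusion.** The gap is real and worth closing. The plan leaves the handling of youth with only a pre-YE survey unstated. Under selective return with a post-on-pre slope between 0 and 1, both readings of the named tests are biased, in opposite directions. Under the assumptions shown (true gain 0.30 SD, 1.65-fold odds per SD), the returners' gain ranges from about 0.27 or 0.33 at correlation 0.7 and 80% return to about 0.21 or 0.40 at correlation 0.5 and 60% return.

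This is a change the plan should make. It does not mean that the pilot or its youth results are invalid. Nor would a mixed model settle the matter completely: it corrects return that depends on the pre-YE score, but not return that depends on the unseen post-YE score or gain. For example, if 30% do not return and gain nothing while returners gain 0.40 SD, the gain in all youth is 0.7 × 0.40 = 0.28, and the model alone would not recover it.

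**What to change.** Add to the Analytical Plan, before the youth data are analysed:

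- Each continuous youth score is analysed by a linear mixed model with time and organization as fixed effects and an unstructured two-visit covariance, on all youth with a pre-YE survey, including those with no post-YE survey.
- The return rate is reported by organization, with pre-YE means of returners and non-returners. This shows whether return was in fact related to the starting score.
- One sensitivity analysis sets the gain to zero in non-returners. It is labelled as one scenario and not as a lower bound.

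The last label matters. If low scorers return more at 80% return and r = 0.5, the zero-gain result is 0.8 × (G + 0.048), which exceeds G whenever G is below 0.8 × 0.048 / 0.2 = about 0.19 SD.

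The cost is a few sentences, a few lines of code and slightly longer reporting, with no new data, visits or participants. The reported gain may be less favourable than a returners-only figure.
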